13.3 Stratification Factors

Patients will be stratified by the MSKCC criteria ([Appendix J](#)) and type of prior therapy before being randomized into the MK2206 arm and the everolimus arm using a ratio of 2:1. The stratified randomization will be conducted through the Clinical Trial Conduct (CTC) website (<https://biostatistics.mdanderson.org/ClinicalTrialConduct>) maintained by the Department of Biostatistics of the University of Texas, M. D. Anderson Cancer Center.

13.4 Statistical Analysis Plan

The primary endpoint, progression-free survival (PFS), is defined as the time interval between date of treatment and date of disease progression, date of death or last follow-up date, whichever occurred first. The probability of PFS be estimated using the Kaplan-Meier method and will be compared between the two treatment arms using stratified log-rank test. Patients' safety data will be summarized by treatment arm, category, severity and relevance.

For secondary analyses, the Kaplan-Meier method will be used to estimate overall survival (OS) and time to failure (TTF), and stratified log-rank test will be used to compare between the two treatment arms. The OS is defined as the time interval between the date of treatment and the date of death or last follow-up, whichever occurred first. The TTF is defined as the time interval between the date of treatment and the date of disease progression, date of death, date of treatment discontinuation due to severe toxicity or last follow-up date, whichever occurred first. Overall response (OR) is defined as CR+PR and logistic regression model will be fit to assess the effect of treatment on the rate of OR.

Since the correlative studies being performed are by nature exploratory, and have not been

performed before in patients with RCC receiving mTOR inhibitors or AKT inhibitors, powering of these endpoints is not possible. Clinical benefit is defined as CR+PR+SD and again, we will fit logistic regression models to assess the effects of treatment, AKT activation, circulating cytokines and angiogenic factors, and karyotype on clinical benefit. The interaction effect between treatment and these exploratory factors will also be evaluated.

For virtual karyotyping, technique specific statistical analyses are outlined in [Appendix G](#).

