1. OBJECTIVES

1.1 Primary Objectives

- 1.1.1 To assess progression free survival (PFS) of vascular endothelial growth factor (VEGF) therapy refractory renal cell carcinoma (RCC) patients who receive either MK-2206 or everolimus.
1. To assess safety of MK-2206 in patients with VEGF therapy refractory RCC

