4. REGISTRATION PROCEDURES

4.1 General Guidelines

See [Appendix K](#): Multi-Center Study Management Plan

Following registration, patients should begin protocol treatment within 5 days. Issues that would cause treatment delays should be discussed with the Principal Investigator. If a patient does not receive protocol therapy following registration, the patient's registration on the study may be canceled. The Study Coordinator should be notified of cancellations as soon as possible.

Except in very unusual circumstances, each participating institution will order DCTD-supplied agents directly from CTEP. Agents may be ordered by a participating site only after the initial IRB approval for the site has been forwarded by the Coordinating Center to the CTEP PIO ([contact]) except for Group studies.

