4.2 Registration Process

Before an institution may begin participation in a M.D. Anderson protocol, all the required steps outlined in [Section 3.3 of Appendix K](#) concerning regulatory documents, must be fulfilled.

Prior to protocol enrollment and initiation of treatment, subjects must sign and date an Institutional Review Board (IRB) approved consent form. Patients at participating institutions should be registered with their institutional central registration first, following each institution's established policies. All patients must then be registered in the M.D. Anderson database, Clinical Oncology Research System (CORe) before beginning treatment. CORe is a clinical research information management system supporting clinical research trials at U.T. M.D. Anderson Cancer Center and collaborative sites across the nation.

At the time of registration, the registrant will be requested to verify the patient's eligibility in

CORE by answering a series of inclusion/exclusion protocol questions and the name of the registering physician. Once patient eligibility has been established, the patient will then be automatically registered and randomized to the appropriate treatment arm. Therapy may then be initiated per protocol guidelines.

Please see [Section 3.3 of Appendix K](#) for registration requirements and data collection guidelines.

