11.1.6 Progression-Free Survival

PFS is defined as the duration of time from randomization to time of progression or death, whichever occurs first.

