13. STATISTICAL CONSIDERATIONS

13.1 Study Design/Endpoints

This is an open-label, multi-center, randomized phase II study. Patients will be randomized using 2:1 ratio to receive either MK2206 or everolimus. The primary endpoint of the study is progression-free survival (PFS), where an event is defined as either disease progression or death. The anticipated median PFS is 4.9 months and 8.2 months for the everolimus and MK2206 arms, respectively. The secondary endpoints include safety, overall survival (OS), overall response rate (ORR) and time to failure (TTF). For the primary endpoint, one interim futility analysis will be performed when a total of 38 events have occurred. The O'Brien-Fleming stopping boundaries using Lan-DeMets spending function will be used for early rejection of H1 (futility boundaries). At the interim look, if the nominal critical point (Z-scale) is less than 0.051, we will terminate trial, reject H1, and conclude that MK2206 has no significant effect on improving PFS. Assuming that the alternative hypothesis holds and trial is continued to completion without interim analysis, 105 patients with 75 events provide 81% power to reject null hypothesis. Since this trial has one interim analysis, 105 patients with 75 events provide 80% power to reject null hypothesis. Please see the detail information for power calculation in [section 13.2](#) sample size / power calculation.

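### Primary PFS starts at randomization in section 11.1.6 but at date of treatment in section 13.4, and no analysis set is named for it

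*Combined protocol and SAP*

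**What the plan says.** On the start of the clock:

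- Section 11.1.6: "PFS is defined as the duration of time from randomization to time of progression or death, whichever occurs first".
- Section 13.4: the primary endpoint "is defined as the time interval between date of treatment and date of disease progression, date of death or last follow-up date", taking the earliest. OS and TTF also start at date of treatment. Only 13.4 defines those two, so they are not in conflict with another section.

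Neither PFS definition appears in the summary of changes, so neither is superseded text.

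On who is analysed:

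- Section 13.4: PFS "will be compared between the two treatment arms using stratified log-rank test". No analysis set is named.
- Section 1.1.1 states the objective for "patients who receive either MK-2206 or everolimus".
- Section 13.5.2, headed Evaluation of Response, requires every patient in the study to be assessed for response, ineligible patients included. It then bases the main response-rate analysis on eligible patients, possibly without the untreated, and rests all conclusions on the eligible patients.

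On the step between allocation and treatment:

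- Section 4.2: once eligibility is established, "the patient will then be automatically registered and randomized to the appropriate treatment arm".
- Section 4.1: "Following registration, patients should begin protocol treatment within 5 days". If no protocol therapy is received, the patient's "registration on the study may be canceled".
- Section 13.1: "This is an open-label, multi-center, randomized phase II study".

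**The concern.** A primary endpoint needs one time origin and one stated set of patients. Here the section that defines the endpoint and the section that specifies its analysis disagree on the origin, and neither states the set.

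The difference matters for patients who are randomized but never start. The arm can be known before the first dose, so whether a patient starts could depend on it. Leaving such patients out would turn a comparison of randomized groups into a comparison of those who chose, or were able, to begin. With 35 planned controls, each one lost is 1/35 = 2.9% of that arm. The definition also decides whose events count toward the 38-event futility look and the 75-event total. If it stays open, the choice could be made after allocation is known.

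**Working it through.** **1. The plan's own figure.** Inputs from sections 13.1 and 13.2: medians 4.9 and 8.2 months, 75 events, 2:1 allocation, one-sided 0.10. The hazard ratio is 4.9/8.2 = 0.598, with log −0.515. The Schoenfeld power is

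Φ(√(75 × 2/3 × 1/3) × 0.515 − 1.282) = Φ(4.082 × 0.515 − 1.282) = Φ(0.82) = 79.4%.

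This has no interim look, so its counterpart in 13.1 is 81% (80% with the look). The figure is reproduced to within 2 points. The start date does not enter the formula.

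**2. The clock shift.** 5 days / 30.44 = 0.16 month, and 0.164/4.9 = 3.4% of the control median. In simulation (105 patients, cut at the 75th event, unstratified, 6,000 trials, delays assumed uniform over 0 to 5 days), equal delays in both arms give 79.4% power on either clock. If only one arm is delayed, changing the clock moves power by about 1.5 points (MK-2206 delayed: 81.1% to 79.6%; everolimus delayed: 79.8% to 81.5%). Simulation error is about half a point per figure.

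**3. The two definitions side by side.**

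| Patient | Section 11.1.6 | Section 13.4 |
|---|---|---|
| Randomized, starts within 5 days | Has a PFS time | Has a PFS time, up to 5 days shorter |
| Randomized, never starts | Has a start date; counts with progression or death, or is censored | Has no start date, so no PFS time and no place in the log-rank test |

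**4. Whether another section settles it.** Section 1.1.1 describes the objective and sets no analysis rule. In 13.5.2 the only sentence broad enough to reach PFS rests conclusions on eligible patients, which is not the same as all randomized patients. The same section bars efficacy conclusions from subsets that drop patients for protocol deviations, but that bar also starts from the eligible. Section 4.1 is silent on analysis. So no section repairs step 3.

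**5. What losing never-starters could do.** The documents give no non-start rate, so any figure is an assumption.

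- *Power.* If a fraction f is dropped and the events are not replaced, 75 × (1 − f) events remain. For f = 3%, 5% and 10% that is 72.75, 71.25 and 67.5 events, and 78.5%, 77.9% and 76.2% power. If the trial still runs to 75 events, nothing is lost.
- *Bias.* As an illustration only, assume that 30% of patients have half the hazard, that strata match prognosis in 75% of patients, and that the 38-event stop applies: simulated one-sided type I error is about 10% with no loss, about 14 to 15% if four good-prognosis controls are lost, and about 7 to 8% if seven good-prognosis MK-2206 patients are lost.

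**The case against.** The strongest reply is that this is untidy drafting with little practical effect. Five days is negligible, eligibility is checked before randomization, the strict 13.5.2 wording concerns response, and most statisticians would analyse all randomized patients anyway. Nothing shows that any patient failed to start.

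Much of this stands. The clock shift is negligible, and no loss is documented. Two stronger readings that a reader might infer also fail:

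- *That the plan prescribes three rival populations (randomized, treated, eligible) for the primary test.* Section 11.1.6 sets a time origin, not an analysis set. Section 1.1.1 is ordinary objective wording. Section 13.5.2 sits under a response heading and opens by including ineligible patients in the assessment. The accurate statement is that no PFS set is named.
- *That section 4.1 removes canceled patients from the analysis and follow-up.* It says neither. Some reasons for not starting (withdrawal, intercurrent illness, change in condition) are already listed in 5.5 and lead through 5.7 to the 3-monthly contact in 5.6, although 5.5 is worded for patients on treatment.

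The reply does not remove the conflict itself. Read literally, section 13.4 gives a never-treated patient no time origin, and good practice by whoever runs the analysis is not a pre-specified rule.

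**Conclusion.** The conflict over the start date is certain, and it should be fixed. It follows directly that under 13.4 a randomized patient who never starts cannot enter the primary test, and that no other section secures a comparison of all randomized patients.

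The size is limited or unknown. The clock shift is trivial provided starts stay close to the 5-day target. The 105 patients, 75 events and about 80% power are unaffected. The bias from omitted never-starters cannot be sized: it could favour either arm if losses depend on both arm and prognosis, and would be negligible if losses are few or balanced.

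A reader might take the illustrative figures to mean that the trial's type I error is inflated to about 15%. The documents do not support that. The prognostic mix, the one-sided losses and the partial match of strata to prognosis are all assumed. The same assumptions with losses from the other arm lower the error, and strata that captured prognosis fully would leave it essentially unchanged.

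**What to change.** - **13.4:** define PFS from date of randomization, to match 11.1.6, and align OS and TTF. State that the primary stratified log-rank test includes all randomized patients in their assigned arm, including those never treated, canceled or later found ineligible. Keep treated-only and eligible-only sets as sensitivity analyses.
- **13.5.2:** state that the eligibility wording applies to response rate.
- **4.1 and 5.6:** state that canceling a registration does not remove a randomized patient from the analysis or, subject to consent, from the existing 3-monthly follow-up. Give the censoring rule for such patients.

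The cost is wording, plus follow-up of any patients who never start. The 8-weekly scans are an on-treatment schedule, so some of these patients will be censored early or counted only at death. One censored at day 0 adds nothing to the log-rank test, so the change recovers only what follow-up yields. Sample size, event target and power stay as planned.

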5.2 Screening and Evaluation On-Study

Within four weeks of study entry:

- All the participants must have signed a consent form agreeing to participate in the study.
- Radiological studies shall include a chest X-ray, and CT scans of the chest and abdomen for the baseline tumor measurement, a CT or MRI of the brain, and a bone scan. Appropriate additional studies should be obtained to fully define the extent and severity of existing or suspected malignant disease.
- A MRI of the spine should be obtained, if there is suspicion of evolving cord or nerve root compression. Spinal cord or nerve root compression syndromes should be managed before trial entry.
- A skeletal survey and a CT scan of the pelvis will be ordered as clinically indicated.
- A 12-lead electrocardiogram

Within two weeks of study entry:

- All patients must undergo a complete history and physical examination, including vital signs, ECOG performance status, recent weight loss, height, and current weight.
- Concurrent non-malignant disease and medical therapy must be documented. On-study forms must be filled out completely.
- All prior anti-cancer treatment must be recorded in proper detail. Any residual toxicity from prior therapies should be recorded by using the grading schema in NCI Common Toxicity Criteria v4.0.
- Patient's MSKCC prognostic criteria will be recorded. ([Appendix J](#)).
- Laboratory studies shall include CBC w/differential, platelet count, chemistry panel (total protein, albumin, alkaline phosphatase, AST and/or ALT, calcium, LDH, total bilirubin, BUN, creatinine, phosphorus, uric acid, sodium, potassium, chloride, carbon dioxide, magnesium, glucose), amylase, lipase, PT and PTT, and urinalysis (pH, specific gravity, ketones, RBC, WBC, bilirubin, and protein). T4, TSH will be obtained. Hemoglobin A1C, fasting glucose, lipid panel and triglycerides will be obtained. Serum pregnancy test in female patients of childbearing potential will also be included and must be negative within 24 hours of enrolling on this study.

Optional studies with patient consent:

- Nephrectomy blocks will be acquired to: a) generate tissue microarray (TMA) to stain for PI3K pathway components and other biologically relevant pathways and molecules and b) perform virtual karyotyping.
- Baseline blood will be drawn for a) plasma and serum analysis of cytokines and angiogenesis factors b) circulating monocytic cells.

Evaluation During Treatment:

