On-study evaluations will consist of the following study activities every four weeks +/- four days (Patients who are progression free after 1 year may have the following performed every 12 weeks +/- 7days):

- History and physical exam by physician, or mid-level provider at each scheduled visit.
- Vital signs (including weight) and ECOG performance status
- Serum chemistry including total protein, albumin, alkaline phosphatase, AST and/or ALT, calcium, LDH, total bilirubin, BUN, creatinine, phosphorus, uric acid, sodium, potassium, chloride, carbon dioxide, magnesium, and glucose at each scheduled visit (+/- 4 days). Hematology including CBC with differential and platelet counts and PT and PTT at each scheduled visit (+/- 4 days). T4, TSH, will be obtained at each scheduled visit (+/- 4 days). Amylase and lipase will be repeated at each scheduled visit as clinically indicated. Fasting lipid panel and glucose will be done every 4 weeks for the first 8 weeks and every 8 weeks thereafter. Cycle 1 Day 1 blood tests will not be done if screening labs were done in the previous 7 days.
- Serum glucose level monitoring for patients every 7 days +/- 2 days for patients on MK2206 during the first cycle of therapy. These measurements do not have to be performed at the study site, but data must be provided to the study team by the patient.
- Hemoglobin A1c levels need to be monitored at the beginning of each cycle for patients on MK2206 who require antihyperglycemic medication.
- Record concomitant medications at each scheduled visit.
- Monitor for adverse events. Treatment-related toxicity (acute and cumulative) will be performed every scheduled visit.
- On C1D1 only, patients randomized to MK-2206 will have an ECG within 4 hours of taking study drug.

Optional studies with patient consent:

- Blood will be drawn for a) plasma and serum analysis of cytokines and angiogenesis factors and b) circulating monocytic cells.

In addition to the above, the following will be performed every eight weeks +/- 7 days (Patients who are progression free after 1 year may have the following performed every 12 weeks +/- 7days):

- Repeat radiologic studies (CT, MRI, Chest x-ray and bone scan as indicated) to evaluate disease progression or response (in accordance with restaging of disease). Studies to confirm a complete response or document progressive disease will be performed as needed.
- 12-lead electrocardiogram (ECG)

End of Treatment

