The following study activities will be completed after treatment has been discontinued for any reason:

- Physical exam.
- Vital Signs including weight
- Radiologic assessment and assessment of response.
- 12-lead electrocardiogram.
- Urinalysis to include: pH, specific gravity, ketones, RBC, WBC, bilirubin, protein, and glucose.
- Serum chemistry including total protein, albumin, alkaline phosphatase, AST and/or ALT, calcium, LDH, total bilirubin, BUN, creatinine, phosphorus, uric acid, sodium, potassium, chloride, carbon dioxide, magnesium, and glucose
- TSH, T4.
- Hematology to include: CBC with differential and platelet count, PT and PTT.
- Record for concomitant medications.
- Monitor for adverse events.

Optional studies with patient consent:

- Blood will be drawn for a) plasma and serum analysis of cytokines and angiogenesis factors b) circulating monocytic cells

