5.6 Duration of Follow Up

Patients will be followed for every 3 months (by telephone, e-mail, clinic visit, or medical record review) after removal from study until death, whichever occurs first. Follow up of a treatment arm will cease once median OS has been reached for that arm. Patients removed from study for unacceptable adverse events will be followed until resolution or stabilization of the adverse event.

If a patient becomes pregnant while on trial and withdraws, the outcome of the pregnancy will be recorded, including the newborn if the pregnancy is carried to full term.

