5.7 Criteria for Removal from Study

Patients will be removed from study when any of the criteria listed in [Section 5.5](#) applies. The reason for study removal and the date the patient was removed must be documented in the Case Report Form.

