10. STUDY CALENDAR

Baseline evaluations are to be conducted within 2 week prior to start of protocol therapy. Scans and x-rays must be done ≤ 4 weeks prior to the start of therapy. In the event that the patient's condition is deteriorating, laboratory evaluations should be repeated within 48 hours prior to initiation of the next cycle of therapy.

| | Screening | Every 4 weeks ^k | Every 8 Weeks ^k | Early Withdrawal/ End of Study |
|---|-------------------|----------------------------|----------------------------|-----------------------------------|
| Informed consent | x ^a | | | |
| Medical history | x ^b | x | | |
| Physical exam | x ^b | x | | x |
| Vital signs | x ^b | x | | x |
| Performance status | x ^b | x | | |
| Weight | x ^b | x | | x |
| Height | x ^b | | | |
| Concurrent meds | x ^b | x | | x |
| CBC w/diff, plts | x ^b | x | | x |
| Serum chemistry | x ^{b, e} | x ^{e, f} | | x |
| HGB A1C | x ^b | | | |
| Fasting Glucose, Fasting Lipid Panel, and triglycerides | x ^b | x ⁱ | x ⁱ | |
| B-HCG | x ^{b, c} | | | |
| PT/PTT | x ^b | x | | x |
| T4, TSH | x ^b | x | | x |
| Amylase, Lipase | x ^b | x ^h | | |
| Hemoglobin A1C | | x ^g | | |
| Urinalysis | x ^b | x | | x |
| EKG | x ^a | x ^j | x | x |
| Adverse event evaluation | <-----> | | | |
| Chest X-Ray | x ^a | | x | x |
| CT Scan Chest/Abdomen | x ^a | | x | x |

| | | | | |
|-------------------------------------|-------------------|---|---|---|
| MRI or CT of Brain | x ^a | | x | x |
| Bone Scan | x ^a | | x | x |
| Other Radiological Scans | x ^{a, d} | | x | x |
| Optional Correlative Blood | x | x | | x |
| Optional Archived Tissue Collection | x | | | |

a Within 4 weeks of study entry

b Within 2 weeks of study entry

c Within 24 hours of study entry

d MRI spine should be obtained if suspicion of evolving cored or nerve root compression. A skeletal survey and/or a CT scan of the pelvis will be ordered as clinically indicated.

e Serum chemistry will include total protein, albumin, alkaline phosphatase, AST and/or ALT, calcium, LDH, total bilirubin, BUN, creatinine, phosphorus, uric acid, sodium, potassium, chloride, carbon dioxide, glucose, and magnesium.

f Serum glucose testing will be done every 7 days for the first cycle of treatment for those patients receiving MK-2206. This can be done at a local physician's office.

g Only for patients on MK-2206 who require anti-hyperglycemic medication.

h Repeated only if indicated

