11. MEASUREMENT OF EFFECT

11.1 Antitumor Effect – Solid Tumors

For the purposes of this study, patients should be re-evaluated for response every eight weeks. In addition to a baseline scan, confirmatory scans should also be obtained not less than 4 weeks following initial documentation of objective response.

Response and progression will be evaluated in this study using the new international criteria proposed by the revised Response Evaluation Criteria in Solid Tumors (RECIST) guideline (version 1.1) [*Eur J Ca* 45:228-247, 2009].

Changes in the largest diameter (unidimensional measurement) of the tumor lesions and the shortest diameter in the case of malignant lymph nodes are used in the RECIST criteria.

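### Section 13.4 ends event-free PFS at an undefined last follow-up date rather than at the last tumor assessment, and no scans are scheduled after the end-of-treatment visit

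*Combined protocol and SAP*

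**What the plan says.** Section 13.4 closes the PFS interval at "date of disease progression, date of death or last follow-up date, whichever occurred first". The last of these is not defined anywhere. The same section uses essentially the same end point for OS. Section 11.1.6 defines PFS by progression or death and gives no censoring rule.

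Imaging is described as follows:

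- Section 5.2, under "Evaluation During Treatment": "In addition to the above, the following will be performed every eight weeks +/- 7 days", followed by the radiologic studies. The interval may lengthen to 12 weeks after a year without progression.
- Section 5.2, end of treatment: "The following study activities will be completed after treatment has been discontinued for any reason", including one radiologic assessment. The Section 10 calendar has the matching column "Early Withdrawal/ End of Study" and nothing after it.
- Section 5.7: "Patients will be removed from study when any of the criteria listed in" Section 5.5 applies. Those criteria include adverse events, withdrawal, intercurrent illness and investigator judgment as well as progression.
- Section 5.6: three-monthly contact "by telephone, e-mail, clinic visit, or medical record review) after removal from study until death". No imaging is named.
- Section 11.1: "patients should be re-evaluated for response every eight weeks". It does not say whether this continues off treatment.

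The note to the response table in Section 11.1.4.3 asks sites to try to document objective progression after treatment ends. It concerns symptomatic deterioration and sets no schedule.

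**The concern.** A telephone call can establish that a patient is alive, so a last-contact date suits OS. It cannot establish that a tumor has not grown. Under Section 13.4 as written, a patient who stops for toxicity, progresses unseen and is later reached by telephone is counted as progression-free up to that call. The patient stays in the risk set and contributes no event until death.

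PFS is the primary endpoint of an open-label trial comparing two drugs on different schedules, so unequal non-progression stops are plausible. If they are unequal and some later progressions go unrecorded, the arm with more of them looks better for a reason unrelated to efficacy. If they are equal, the arms are diluted alike and the test loses power. In addition, two analysts could read the phrase differently and obtain different primary results.

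**Working it through.** **Inputs from the documents (Sections 5.2, 13.1, 13.2).** Medians 4.9 and 8.2 months; 2:1 allocation, 70 MK-2206 and 35 everolimus; one-sided alpha 0.10; 75 events; 4 patients per month; about 29 months in total; futility stop if Z < 0.051 at 38 events; scans every 8 weeks.

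**The plan's own figure.** With exponential PFS, HR = 4.9/8.2 = 0.598 and |ln HR| = 0.515. Schoenfeld power is Φ(|ln HR| × √(D × p × (1 − p)) − z), with D = 75, p = 2/3, z = 1.2816:

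0.515 × √(75 × 2/9) − 1.2816 = 0.515 × 4.082 − 1.2816 = 0.82, and Φ(0.82) = 0.794.

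The plan states 81% without and 80% with the interim look, so its figure is reproduced.

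**Assumptions not in the documents.**

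- Stop rate: the share stopping before progression, set at 10 to 30% per arm and independent of progression unless stated. The 30% in Section 13.1 is a toxicity stopping threshold, not a forecast.
- Share found: the proportion of stopped patients who keep 8-weekly scan dates afterwards; the others have none.
- Median survival after progression: 8 to 12 months (8 to 14 in the runs without the interim look).

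**Simulation.** Exponential progression, 8-weekly detection, deaths counted, rejection if Z > 1.2816 at 75 events, unstratified test, 3,000 to 5,000 trials per scenario (Monte Carlo SE about 0.01 or less). With no stops, type I error is 0.10 to 0.11 and power 0.78 to 0.79 with the look. The ranges below cover separately coded runs, with the look applied and half found. Stops are everolimus/MK-2206.

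| Stops | Quantity | Section 13.4 as written | Censored at last scan |
|---|---|---|---|
| 10%/20% | type I error | 0.12–0.14 | 0.09–0.11 |
| 10%/30% | type I error | 0.15–0.17 | 0.09–0.11 |
| 10%/10% | power | 0.74–0.76 | 0.77–0.80 |
| 20%/20% | power | 0.71–0.73 | 0.76–0.80 |
| 20%/10% | power | 0.68–0.73 | 0.77–0.80 |

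**Sensitivity of the as-written rule.**

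- 75% found: type I error 0.10 at 10%/20% and 0.12 at 10%/30%.
- None found (upper bound): 0.15–0.16 and 0.23–0.29 with the look; 0.17–0.19 and 0.26–0.32 without it.
- More stops on everolimus, half found: 0.079 at 20%/10% and 0.055 at 30%/10%, so the test becomes conservative.
- Equal stops, even with none found and no look: type I error stays at about 0.10 to 0.11.
- Stratified test with three assumed strata (hazards 0.67/1/1.5), half found: type I error 0.12 and 0.15 in the first two rows; power 0.73 and 0.71 at equal 10% and 20% stops, against 0.76 with none.

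**Toxicity rule of Section 13.1 added (one simulation only).** If every MK-2206 stop is a Grade 3+ toxicity stop, type I error as written is 0.11–0.12 at 10%/20% and 0.10–0.11 at 10%/30%. Last-scan censoring under the same rule gives 0.09 and 0.06–0.07, because halted trials lower both. If half of the stops are toxicity stops, the as-written figures are 0.12 and 0.15–0.16. The printed boundaries have exact crossing probabilities of 0.034 and 0.21 at true rates of 20% and 30%, where Table 6 prints 0.047 and 0.288. The adjusted figures could therefore be slightly lower.

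**Events.** With half found and the planned effect, both censoring rules give the same 70–72 events by 29 months (73 with no stops) and reach 75 at about 30–31 months. Moving the censoring date loses no events; the shortfall comes from missed progressions.

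**The case against.** The strongest case against is that the size rests wholly on assumed rates. The documents forecast neither stops by arm nor the share of later progressions found. With 75% found, the excess is at most 0.02. The direction is also open: everolimus has many discontinuation triggers in Section 6.2, and more stops there make the test conservative. If MK-2206 stops are mainly severe toxicity, the trial's own safety rule brings overall type I error back to about nominal. This stands as a limit on the numbers. It does not supply the missing definition, and the reverse direction costs power.

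Second, off-treatment detection is not excluded. Section 11.1 states no on-treatment limit, and clinic visits or record review may surface outside scans. This makes the none-found bound remote, but none of these texts schedules a scan or links the censoring date to one. The data-entry list in Appendix K, Section 3.3 names no last-assessment date, but that appendix is a generic template and shows little about this trial's forms.

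Third, last-scan censoring is not a complete cure. It does not recover missed progressions, and it assumes stopping is unrelated to progression risk. If progression runs twice as fast after a stop (10%/30%, half found), null rejection is 0.06–0.07 under last-scan censoring, 0.10–0.12 as written, and 0.04–0.05 with complete scanning. This stands, and is the reason to pair the rule with sensitivity analyses.

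**Conclusion.** The concern holds and should be fixed. The text gap needs no assumptions: the censoring date for the primary endpoint is undefined, is not linked to a tumor assessment, and can be set by a contact at which no disease assessment takes place. The consequences are conditional. With half of post-stop progressions found, type I error reaches about 0.12 to 0.17 when MK-2206 has 10 to 20 percentage points more stops than everolimus, and power falls by roughly 3 to 8 points at equal stops of 10 to 20% (0.78–0.79 down to 0.71–0.76). Confidence is high for the gap and the conditional arithmetic. Whether bias would occur, and in which direction, cannot be told from the documents.

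TTF is a useful cross-check but not a correction. In one simulation with every stop recorded as severe toxicity at 10%/30% (half found), TTF was also positive in only 3% of false-positive PFS trials, but in only 44% of trials that detected a real PFS effect.

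**What to change.** In Section 13.4, state that patients without documented progression or death are censored for PFS at their last adequate tumor assessment. Keep last follow-up for OS, and continue to count deaths as PFS events. State also how scans taken after another anticancer therapy are handled. If last follow-up already meant last disease assessment, the same sentence settles it.

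At the existing three-monthly contacts, record dates and results of all off-treatment scans, negative as well as positive. In one simulation, entering only positive scans gave null rejection of 0.07 at 10%/30% (half found), against 0.09 with all entered.

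Report the last-follow-up rule as a sensitivity analysis. Optionally add a second that censors, at the last scan, deaths occurring after two missed scheduled assessments.

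The cost is one sentence, one form field and one or two tables. No imaging is added. The downside is power of 0.74–0.77 under last-scan censoring at 10%/30%, together with the reliance on uninformative stopping noted above.
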